3.1. Study Outcomes

The aim of this study is to describe the use of POCUS and its role in the diagnostic and therapeutic process in general medicine.

- Description of the use of POCUS through indication, organs scanned, findings, frequency , time consumption.
- Analysis of the role of POCUS in the diagnostic process: change of diagnostic hypotheses and change of certainty in the main diagnostic hypothesis.
- Analysis of the role of POCUS in the therapeutic process: change in the care pathway/referral plan and the therapeutic initial plan.

This is an observational study without any intervention.

3.2. Study design

This study is an observational, prospective and multicenter study. General Practitioners (GP) who were recruited had to complete a questionnaire with a "pre-post" design with questions about consultation before POCUS (Q1-Q14), a timelog for ultrasound performance and additional questions about the consultation after POCUS (Q15-Q29).

3.2.1. Questionnaire BEFORE POCUS

Question Number	Question	Possible Answers	Answer format
Q1	GP ID Number	A à Z or AA à AM	1 or 2 letters
Q2	Patient ID number	A1 to Z26 and AA1 to AM26	1 or 2 letters follow by 2 digits
Q3	Date	2022-11-17 to 2024-06-06	AAAA-MM-JJ
Q4	Patient gender	Man, Woman or Other	Single answer question
Q5	Patient Age	0 to 120	Number with 1 to 3 digits
Q6	Setting of POCUS	
- At patient's home- At medical office- Other, to specify	Single answer question
Q7	What is the main reason to use POCUS in this patient ?	
- Answer to a specific clinical question (answer yes/no/maybe) and document the answer in patient's medical record- Therapeutic Education- Follow or Control an echographic	Multiples answers question

		
signal
 
 - Screen an asymptomatic patient - Training without clinical benefit - Analyse and describe in detail an anatomical structure with multiples organs and edit a complete report 	
Q8	Anatomical areas planned to be scanned	
 - Abdominal/Urologic - Gynecologic-Obstetrical - Musculoskeletal - Vascular - Thoracic - Other/Superficial 	Multiples answers question
Q9	Organs planned to be scanned	
 - Gallbladder, Kidneys, Liver, Spleen, Pancreas, Morrisson's pouch, Bladder, Prostate, Testes, Douglas pouch, Other abdominal structures - Uterus, Ovaries, Gestational sac, Embryo, Douglas pouch, Other gynecological/obstetric structures - Joint, Joint infiltration, Muscle, Tendon, Bone, Other musculoskeletal structures - Aorta, Deep veins of the lower limbs, Carotid arteries, other vascular structures - Lungs, Pleura, Heart, Other thoracic structures - Thyroid, Tissues, Lymph nodes, Breasts, Other superficial structures 	Multiples answers question
Q10	What is the main tentative diagnosis for this patient ?	ICPC2 code	1 letter followed by 2 digits
Q11	Are there any other possible tentative diagnoses in this case ?	Yes / No	Single answer question
Q12	Second, Third and Fourth tentatives diagnoses	ICPC2 code	1 letter followed by 2 digits
Q13	GP's overall / referral plan for the patient before POCUS use	
 - Acute admission to hospital - Subacute referral (2-3 days) to hospital - Elective referral to hospital - Subacute referral (2-3 days) to specialist - Elective referral to specialist - Referral to radiology, and which imaging prescribed (radiography, échography, Scanner, IRM) - Outpatient follow-up - No plan for follow-up - Other referral (physiotherapist...), to 	Multiples answers question

		specify	
Q14	Which treatment will you initiate at this stage ?	
 - Medication - I will refer for treatment - I will initiate other treatment - No treatment - Other 	Multiples answers question

3.2.2. Questionnaire AFTER POCUS

Question number	Question	Possible Answers	Answer format
Q15	How much time did you use on the POCUS examination ?	Minutes	Number with 1 to 3 digits
Q16	Anatomical areas scanned	
 - Abdominal/Urologic - Gynecologic-Obstetrical - Musculoskeletal - Vascular - Thoracic - Other/Superficial 	Multiples answers question
Q17	Organs scanned	
 - Gallbladder, Kidneys, Liver, Spleen, Pancreas, Morrisson's pouch, Bladder, Prostate, Testes, Douglas pouch, Other abdominal structures - Uterus, Ovaries, Gestational sac, Embryo, Douglas pouch, Other gynecological/obstetric structures - Joint, Joint infiltration, Muscle, Tendon, Bone, Other musculoskeletal structures - Aorta, Deep veins of the lower limbs, Carotid arteries, other vascular structures - Lungs, Pleura, Heart, Other thoracic structures - Thyroid, Tissues, Lymph nodes, Breasts, Other superficial structures 	Multiples answers question Some free text to specify which organs were explored by GP when they check "Other" boxes
Q18	Were you able to produce ultrasound images of the relevant structures of [each selected organ Q17]?	Yes / No	Single answer question
Q19	What did you find ?	
 - Certain positive findings - Uncertain positive findings - Certain negative findings - Uncertain negative findings - Incidental findings 	Multiples answers question Free text to specify which incidental finding GP found

Q20	Have your diagnostic hypotheses changed?	Yes / No	Single answer question
Q21	What is the diagnostic hypothesis for the patient now ?	ICPC2 Code	1 lettre followed by 2 digits
Q22	Are there any other possible diagnostic hypotheses for this patient ?	Yes / No	Single answer question
Q23	Second, third and fourth diagnostic hypotheses after POCUS performed	ICPC2 Code	1 letter followed by 2 digits
Q24	Were you able to eliminate certain hypotheses ?	Yes / No	Single answer question
Q25	How is your confidence in your main diagnostic hypothesis, after you have used POCUS ?	
 - Highly increased confidence - More confidence - Unchanged confidence - Less confidence - Highly reduced confidence 	Single answer question
Q26	Has your overall / referral plan changed ?	Yes / No	Single answer question
Q27	What is your overall / referral plan for this patient now ?	
 - Acute admission to hospital - Subacute referral (2-3 days) to hospital - Elective referral to hospital - Subacute referral (2-3 days) to specialist - Elective referral to specialist - Referral to radiology, and which imaging prescribed (radiography, échography, Scanner, IRM) - Outpatient follow-up - No plan for follow-up - Other referral (physiotherapist...), to specify 	Multiples answers question
Q28	Has your initiated treatment for this patient changed ?	Yes / No	Single answer question
Q29	Which treatment will you initiate at this stage ?	
 - Medication - I will refer for treatment - I will initiate other treatment - None - Other 	Multiples answers question

GP's characteristics

3.2.3. Questionnaire

Each GP has to complete the following questionnaire to verify their eligibility for the study and to collect informations about their POCUS practice :

Question Number	Question	Possible Answer	Answer format
Q1*	Name and Surname	NAME Surname	Free text
Q2*	Email address	/	Free text
Q3*	Phone number	/	10 digits
Q4*	Do you practice general practice?	Yes / No	Single answer question
Q5*	Medical office address	/	Free text
Q6*	Postal Address	/	Free text
Q7*	How many half-days do you practice general practice, including "SOS Médecins" and home visits ?	1-14	Number with 1 or 2 digits
Q8*	Do you work at "SOS Médecins" ?	Yes / No	Single answer question
Q9*	Do you practice POCUS in general practice or at home visits ?	Yes / No	Single answer question
Q10*	How many years have you been practicing ultrasound?	1-99	Number with 1 or 2 digits
Q11*	How many times per consultation day do you use ultrasonography on average ?	1-999	Number with 1 to 3 digits
Q12*	What type of ultrasonography device do you use ?	
 - Don't have any one - Portable device - Ultra portable device - Fixed device - Specify the brand and the model 	Multiples answers question
Q13*	Which kind of probe do you have ?	
 - cardiac/phased array - convex/curvilinear/abdominal - superficial/linear - endovaginal/endocavitory - Other : specify 	Multiples answers question

Q14*	Which anatomical area do you usually explore ?	
 - Abdomen - Muskuloskeletal - Urologic area - Gynecological - Obstetric - Heart - Vascular - Lungs - Thyroid - Tissues - Eyes 	Multiple answers question
Q15*	Have you received ultrasound training?	Yes / No	Single answer question
Q16*	What kind of training have you received ?	
 - Name of degree - Modules followed - Year of obtaining - Number of training hours (theoretical/practice) - Number of supervised exams (if it's relevant) 	Free text
Q17*	Are you a trainer in a course about ultrasonography ?	
Yes / No
 
Specify the organization
	
Single answer question
 
Free text

3.2.4. Supplementary questions

Supplementary questions were asked after discussion with GPs and research team, about :

Q18*	Practice of scheduled ultrasound examinations	Yes / No	Single answer question
Q19*	Frequency of ultrasound billing/fees	All, some of them or none	Single answer question
Q20*	University internship supervisor status	
Yes / No
 
Extern, Intern level 1, Intern level 2, intern on a women's or child's health internship
	
Single answer question
 
Multiple answers question

Q21*	Member of a department of general practice in university	Yes / No	Single answer question

4. Descriptive Statistics

4.1. GPs characteristics

- Gender : Number and proportion de GPs
- Median Age, Interquartiles
- Geographic region of exercise : Number and proportion of GPs
- Setting : Medical office / Home visits / Other (Number and proportion of GPs)
- Experience in ultrasound (years) : median/interquartiles
- "SOS Médecins" network participation : Number and proportion of GPs
- Ultrasound device type : Number and proportion of GP per group (portable, ultra portable and fixed)
- Number of ultrasound devices per GP : médian / interquartile
- Probe type : Number and proportion of GP per group ("superficial/linear", "abdominal/curvilinear", "cardiac/phased-array", "endocavitory", "mixed/multi-probe" and "Other")
- Number of probes per GP : median / interquartile
- Educator of ultrasound in general practice/trainer: Number and proportion of GP
- University internship supervisor status : number and proportion of GP welcoming at least one student (extern, intern level 1, intern level 2, an intern on a women's or child's health internship)
- Faculty/member of a department of general practice in university : number and proportion of GPs
- Practice of scheduled ultrasound examinations : Number and proportion of GPs
- Fees/Billing of ultrasound studies : Number and proportion of GPs per group ("all", "some of them", "none")

4.2. Education/training in ultrasound and applications of POCUS

Visual support : Table

- Number of education/training programs : median/interquartile
- Type of education/training programs : Number and proportion of GP per group :
 - o long (> 1 year), short, others lengths
 - o University degrees, public trainings, private degrees, self study
- Anatomical areas scanned by GPs : Number and proportion per group
- Number of anatomical areas usually scanned : median/interquartile

4.3. Patients's characteristics

Visual support : Flow Chart

- Number of patients eligibles for a POCUS
- Number of patients excluded by GPs, exclusion criteria described
- Number of patients included in the study
- Number of patients excluded after data verification, exclusion of data errors

- Number of patients included in analysis
- Number of patients excluded because of an ultrasound duration of less than 60 seconds
- Number of patients included in “pre-post” analysis
- The difference for age and gender between the excluded patients by GPs according to the exclusion criteria and the included patients in the study will be tested by chi2 test.

Visual support : Table

- Gender : Number and proportion of patients
- Age : médian/interquartile
- Place of performing POCUS : number and proportion of patients per group (“medical office”, “patient’s home”, “other”)
- Geographic region of performing POCUS : Number and proportion of patients per region
- Number of patients included per GP : Median/interquartile

4.4. POCUS’s characteristics

Visual support : Table

- Frequency of POCUS use :
 - o Described according to the distribution, if normal by mean+95%CI if not normal by the median number of POCUS per day / Interquartile,
 - o Proportion of consultations with POCUS during the study
- Indications of POCUS (Q7) : Number and proportion of POCUS per indication
- Duration of POCUS use per consultation (Q15) : Described according to the distribution, if normal by mean+95%CI, if not normal by the median / interquartile
- Certainty of ultrasound findings (Q19) :
 - o Number and proportion of POCUS examinations with at least one certain ultrasound finding
 - o Number and proportion of POCUS examinations with at least one uncertain ultrasound finding
 - o Number and proportion of POCUS examinations with at least one certain positive finding, one certain negative finding, one uncertain positive finding, one uncertain negative finding
- Image relevance (Q18) : Number and proportion of relevant images obtained (total and per organ scanned). Description of reasons for lack of acquisition.

4.5. Anatomical areas scanned

Description of the proportion of POCUS for each kind of anatomical area (Q16).

Visual support : Histogram

Anatomical areas that we plan to distinguish are : Abdominal, urologic, musculoskeletal, pulmonary, cardiac, venous, arterial, thyroid, soft tissues, breast and others.

4.6. Organs scanned

Description of the proportion of organs scanned in POCUS examinations (Q9, Q17).

Visual support : Grouped histogram with organs scanned in abscissa and number of consultations concerned before and after POCUS in ordinate.

Organs scanned will be described in 36 different categories (ref Q9 and Q17).

We will describe the number and proportion of POCUS examinations in which GPs scanned more, fewer or as many organs as initially planned.

4.7. POCUS duration use per consultation

Description of median duration of POCUS exams (Q15).

Visual support : box plot.

We will describe the duration of POCUS by anatomical area for patients having a scan of a single anatomical area. If at least 2 anatomical areas were scanned in the same ultrasound, we will group these patients in a new category called “>1 anatomical area”.

The less scanned anatomical areas (less by 5 POCUS performed) will be grouped in a “Others” category.

4.8. Incidental findings

We will describe the incidental findings and their proportion(Q19).

4.9. Diagnostic Hypotheses

We will list the total number of ICPC-2 codes before and after performing POCUS (Q10, 12, 21, 23).

Visual support :

- *Table with number of occurrences for each ICPC-2 code listed during the study, depending on whether it appears as a primary or secondary hypothesis before or after POCUS performing.*
- *Histogram of the most used ICPC-2 codes in the study.*

4.10. Confidence in the final main hypothesis

Number and proportion of POCUS examinations leading to an increase in confidence, to a decrease in confidence or not leading to a change in confidence in the main final hypothesis (Q25).

We will quantify situations where the confidence was decreased, analyse these situations in terms of type of organ scanned, duration of POCUS and change in the diagnostic hypothesis's number before and after POCUS examination.

5. Comparative Statistics

5.1. Change in diagnostic hypotheses

Visual support : Table of consultation number with 1, 2, 3 or 4 diagnostic hypotheses before and after POCUS examination

- Proportion of consultations with a change in the main diagnostic hypothesis
- Proportion of consultation with a global change in diagnostic hypotheses (Q20)
- Number of ICPC-2 code classed as “symptom” before POCUS, and number of classed as “symptom” after POCUS

A global modification of diagnostic hypotheses corresponds to a modification, a removal or an addition of a diagnostic hypothesis after POCUS, or a change in the main hypothesis.

We will study the relationship between the reduction of the number of diagnostic hypotheses and increase in the confidence with a Chi2 test if the numbers in each group are greater than 5. If the number in each group is lower than 5, we will use a Fisher test.

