The diagnostic hypotheses are registered as detailed free text in the questionnaire. The corresponding ICPC-2 (International Classification of Primary Care-2) codes will be coded from the free text by the research team.

The observed change in the diagnostic hypotheses will be described by the frequency of declared diagnostic hypotheses changes and the overall registered change in the ICPC-2 codes. Overall registered change in the ICPC-2 codes are defined as:

- Change in the ICPC-2 code of the main diagnostic hypothesis after US
- Change in all possible ICPC-2 diagnostic hypotheses after the use of POC-US
- Change in the total number of diagnostic hypotheses
- Change from symptom diagnosis to disease diagnosis after POC-US

b. Change in confidence

The GPs are asked to register any change in their confidence in the diagnostic hypothesis after the use of POCUS by choosing one of the following variables on an ordinal scale:

- increased confidence
- more confident
- unchanged confidence
- less confident
- reduced confidence

IV. Role of POCUS in the therapeutic process

We will describe the patient's plan before and after POCUS and the planned treatment before and after POCUS. We will describe the relationship between the ultrasound findings and the change in the patient management (diagnostic process, treatment, care pathway). The diagnostic and therapeutic modifications will be described by the frequency of responses or by the change in the total number of responses.

The statistical analysis will be descriptive. Data collection will mainly be done using nominal variables. However, the variable "GP's confidence in the diagnostic hypotheses" will be

measured by an ordinal variable, "the duration of the examination" and "the patient's age" by a continuous variable.

The categorical variables will be described using contingency tables and Chi-2 test and Fisher's exact test will be used to test the relationship between the variables. If the continuous variables follow the normal distribution, they will be described with means and either a standard deviation or a 95% confidence interval of the mean. If they are not normally distributed, they will be described with a median and interquartile range.

a. Change in the therapeutic plan for the patient

The GPs will register their plan for the patient by choosing one or more of the following categorical variables before using POC-US:

- acute admission to hospital
- subacute referral to hospital

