5.6. Global change in patient care

We will consider a global change if there was a change in the main hypothesis, a global change in diagnostic hypotheses, a change in treatment plan, in patient's orientation plan or in imaging or exams prescription.

Visual support : Table (continuation of the table 5.1)

Number and proportion of consultations with a global change in patient care.

For all comparative analyses, we will consider consultations with a measured POCUS duration greater than 60 seconds.

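### SAP 5.1's reduction-versus-confidence test counts single-hypothesis consultations as not reduced, and its unpaired symptom totals do not in general give the protocol's symptom-to-disease change

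*SAP*

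**What the plan says.** **Reduction and confidence.** SAP 5.1 plans this analysis: "We will study the relationship between the reduction of the number of diagnostic hypotheses and increase in the confidence with a Chi2 test", with Fisher's test for small groups. It names no denominator. SAP 5.6 gives the one general restriction: "For all comparative analyses, we will consider consultations with a measured POCUS duration greater than 60 seconds". Before the scan, Q11 asks "Are there any other possible tentative diagnoses in this case" and allows the answer No, so a consultation may start with a single hypothesis. The count is displayed as "Table of consultation number with 1, 2, 3 or 4 diagnostic hypotheses before and after POCUS examination". Confidence is asked once, after the scan (Q25). SAP 4.10 relates confidence to the change in number only for falls in confidence: "We will quantify situations where the confidence was decreased".

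**Symptom to disease.** Protocol Results III.a lists, among the registered changes in ICPC-2 codes, "Change from symptom diagnosis to disease diagnosis after POC-US". SAP 5.1 plans "Number of ICPC-2 code classed as “symptom” before POCUS" and the same total after the scan. Two other outputs bear on this: the SAP 4.9 table of occurrences per code, split by primary or secondary and by before or after, and SAP 5.1's "Proportion of consultations with a change in the main diagnostic hypothesis".

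**The concern.** The not-reduced group mixes consultations that could not reduce with those that could and did not. If GPs who start with one hypothesis gain confidence at a different rate from those who start with several, that difference enters the comparison. It can produce an association where narrowing is unrelated to confidence, or hide a real one. Readers will naturally take a significant result to be about narrowing. No other planned output separates the two kinds of non-reducer: the 1-to-4 table carries no confidence, and SAP 4.10 covers only falls in confidence.

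The second gap concerns an item that the protocol lists under its diagnostic aim. A fall in the total of symptom codes may mean that symptoms became diseases, or only that secondary symptom codes were dropped. Flows in opposite directions also cancel.

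**Working it through.** **1. Can a single-hypothesis consultation reduce?** The SAP 5.1 table starts at 1 both before and after. Q21 asks for a code after the scan and shows no 'none' option. No sentence forbids zero hypotheses afterwards, but nothing provides for it. These consultations therefore count as not reduced.

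**2. A small example (assumed counts).** Take 200 consultations starting with two or more hypotheses: 100 reduce, 100 do not, and confidence rises in 80% of each group. Chi-square = 0, p = 1.00. Add 200 single-hypothesis consultations with confidence raised in 60% (120 against 80). The table becomes 80/20 for reduced and 200/100 for not reduced:

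chi-square = 400 × (80×100 − 20×200)² / (100 × 300 × 280 × 120) = 6.35, p = 0.012.

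**3. Frequency at the planned size.** The protocol expects 660 to 1,320 scans, 70% includable: 0.70 × 660 = 462 and 0.70 × 1,320 = 924, before the 60-second exclusion. All other inputs are assumed. Starts at 1/2/3/4 are 40/30/20/10%. There are 20,000 simulated studies per setting, with independent consultations, alpha 0.05 and no continuity correction. CMH is the Cochran-Mantel-Haenszel test stratified by starting number.

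- Setting A: no association at a given starting number; 60% reduce at every start of two or more.
- Setting B: no association at a given starting number, but starts at 2 (50% reduce, 85% confident) differ from starts at 3–4 (80% reduce, 75% confident).
- Setting C: a real association; 60% reduce, confidence 85% in reducers against 75% in non-reducers, OR = (0.85/0.15)/(0.75/0.25) = 1.89.

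| Setting | Planned test, n = 462 / 924 | Starts ≥ 2, unstratified | CMH |
|---|---|---|---|
| A, singles 85% v multiple 85% | 5% / 5% | – | 5% |
| A, 80% v 85% | 13% / 22% | – | 5% |
| A, 75% v 85% | 37% / 65% | – | 5% |
| A, 85% v 75% | 36% / 61% | – | 5% |
| B, singles 85% | 30% / 51% | 10% / 15% | 5% / 5% |
| B, singles 75% | 6% / 8% | 10% / 15% | 5% / 5% |
| C, singles 90% | 5% / 6% | – | 55% / 83% |
| C, singles 75% | 73% / 96% | – | 54% / 83% |

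The third row by hand: confidence among the not-reduced is (0.24×0.85 + 0.40×0.75)/0.64 = 0.7875, against 0.85 in reducers, so OR = (0.85/0.15)/(0.7875/0.2125) = 1.53 although narrowing has no effect. For setting C with singles at 90%: (0.24×0.75 + 0.40×0.90)/0.64 = 0.844, and the OR falls from 1.89 to 1.05.

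**4. Clustering.** The 5% for CMH depends on independent consultations. The expected totals imply 660/22 = 1,320/44 = 30 GPs. With assumed GP-level tendencies (logit SD 1, correlation 0.5) and no within-GP association, CMH rejects in about 23% at 462 and 36–37% at 924, against 15–16% and 26–27% for the planned test. With weak tendencies both stay near 5%.

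**5. What the symptom totals determine.** Per 100 main hypotheses, assume 40 symptom codes before and 30 after, with c mains changed. Let x be symptom-to-disease and y disease-to-symptom. Then x − y = 10, x + y ≤ c and x ≤ 40, so x runs from 10 to min(40, (c + 10)/2):

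- c = 20: 10 to 15
- c = 30: 10 to 20
- c = 40: 10 to 25

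These bounds use only the symptom totals and the proportion changed. The code-level counts of SAP 4.9 can tighten them. Suppose no symptom code gains, disease code D1 goes from 50 to 40, disease code D2 from 10 to 30, and 20 mains change. The net shift is already 20, so no code both gains and loses, and x is exactly 10. In general the counts do not fix x.

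**The case against.** The strongest reply on the first part is that the all-consultation test is a legitimate test of a marginal association, and SAP 5.1 promises only to study a relationship. That stands. A reader might infer that the test is invalid or that its type I error is inflated. The documents do not support this: the rejection rates above are not errors for the marginal question, only for a reading about narrowing. It also stands that inclusion of single-hypothesis consultations follows from silence, that every rate is assumed, and that the planned test has more power when singles behave like non-reducers.

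A reader might also infer that stratifying by starting number restores a 5% test. It does so only without appreciable clustering by GP.

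On the second part, Protocol Results IV says that diagnostic modifications will be described by response frequencies or by changes in total number, and symptom totals are such a change. The totals are therefore a permitted summary, but that does not make them a count of transitions from one category to the other. A reader might infer that the planned outputs can never settle the count. That is too strong, since code-level counts sometimes do. It is also fair that the protocol item is not expressly limited to the main hypothesis.

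**Conclusion.** Both parts hold in limited form. The planned test is valid as a marginal association, but it does not isolate narrowing if confidence differs by starting number. With equal confidence at every start, including the singles does no harm under the null. The documents give neither the share of single-hypothesis consultations nor any confidence rate, so the illustrated range (5% to 65% significant with no association at a given starting number, or a real OR of 1.89 reduced to 1.05) is not a forecast.

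The symptom totals, even with the other planned counts, do not in general determine the symptom-to-disease change. This needs no assumed rate. The gap is in the output, not in the data.

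Priority is low: the study is mainly descriptive, and no sample size or primary decision rests on either point.

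**What to change.** 1. Add a per-consultation before/after table of the main hypothesis (Q10 against Q21) as symptom or disease, with the number and proportion moving from symptom to disease. If the protocol item is read more widely, add the same for any hypothesis.
2. Report reduction against confidence among consultations with at least two hypotheses before the scan, stratified by starting number (2, 3, 4), with an analysis that allows for clustering by GP. Restriction alone is not enough (setting B). Describe confidence in single-hypothesis consultations separately. Label any all-consultation test as marginal.
3. For both, state that Q10 and Q12 are carried forward where Q20 is No, because Protocol III.a has GPs specify diagnoses after the scan only if these changed.

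**Cost.** No new data are needed: Q10–Q12, Q20–Q23 and Q25 hold them per consultation. The paired table costs nothing beyond wording. The stratified analysis can lose power: if singles behave like non-reducers, 0.73 falls to 0.54 at n = 462, and 0.96 to 0.83 at n = 924, before any allowance for clustering. The SAP is dated 05/22/2025 and the Q3 date range ends on 2024-06-06, so the change should be reported as made after data collection.
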